4.2 Exclusion Criteria

Participants who meet any of the following criteria will not be eligible for the study:

1. Blood culture, or any other culture, positive for *C. krusei*
2. Life expectancy of <7 days in the opinion of the Investigator
3. Severe or moderate hepatic impairment (Child-Pugh Score >6 points) at any time during 2 weeks prior to dosing. The Child-Pugh score of >6 is applicable to patients with hepatic dysfunction and cirrhosis only.
4. Baseline neurological conditions such as abnormal movements or convulsive disorders
5. Human immunodeficiency virus-infected patients who are receiving antiretroviral therapy that are moderate to strong inducers of CYP3A4, or who have detectable viremia, or who have had an active opportunistic infection within 6 months prior to Screening
6. Alanine aminotransferase or aspartate aminotransferase $\geq 5 \times$ upper limit of normal (ULN)
7. Total bilirubin $> 3 \times$ ULN, unless isolated hyperbilirubinemia or due to documented Gilbert's disease.
8. Female patient is pregnant or lactating
9. Inappropriate fungal infection source control (e.g. persistent indwelling catheters or intravascular devices)
10. Investigational drug administered within 30 days prior to dosing or five half-lives whichever is longer
11. Concomitant use of medication that is a strong inducer of CYP enzymes (e.g. rifampin, carbamazepine, phenytoin, rifabutin, efavirenz, nevirapine, phenobarbital, modafinil, nafcillin, St. John's Wort, and enzalutamide)
12. Any other condition or laboratory abnormality that, in the opinion of the Investigator, would put the patient at unacceptable risk for participation in the study or may interfere with the assessments included in the study
13. Diagnosis of deep-seated *Candida*-related infections causing hardware associated septic arthritis, osteomyelitis, endocarditis, myocarditis, hepatosplenic candidiasis, or a central nervous system infection or site of infection that would require antifungal therapy to exceed the maximal duration of study drug treatment (i.e. 6 weeks [42 days])

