APPENDIX D: DRUG-INDUCED LIVER INJURY CRITERIA

For patients with normal liver transaminases and bilirubin at baseline:

If patients with normal baseline liver indices develop new elevations of aspartate aminotransferase (AST) or alanine aminotransferase (ALT) or alkaline phosphatase (ALP) >3 x upper limit of normal (ULN) or total bilirubin (TBL) >2 xULN values during the study, repeat testing should be performed within 48 to 72 hours. Investigators should also ask the patient if he/she has symptoms.

If there are persistent elevations (ALT or AST >3 x ULN or TBL >2 x ULN) upon repeat testing, then close observation (as described below) should be implemented and discontinuation of drug should be considered.

Drug should be discontinued, and the patient followed until resolution of symptoms or signs in the following situations:

- ALT or AST >8 x ULN
- ALT or AST >5 x ULN for more than 2 weeks.
- ALT or AST >3 x ULN and (TBL >2 x ULN or INR >1.5)
- ALT or AST >3 x ULN with the appearance of fatigue, nausea, vomiting, right upper quadrant pain or tenderness, fever, rash, and/or eosinophilia ($>5\%$).

For patients with elevations in baseline transaminases or bilirubin:

If patients with abnormal baseline liver indices develop elevations of AST or ALT >2 x baseline or TBL >2 x baseline values during the study, repeat testing should be performed within 48 to 72 hours. Investigators should also ask to the patient if he/she has symptoms.

If there are persistent elevations (ALT or AST >2 x baseline or TBL >2 x baseline values) upon repeat testing, then close observation (as described below) should be implemented and discontinuation of drug should be considered.

Drug should be discontinued, and the patient followed until resolution of symptoms or signs in the following situations:

- If baseline measurements were <2 x ULN, discontinue if ALT or AST increases to >5 x baseline measurements.
- If baseline average measurements >2 x ULN, discontinue if ALT or AST increases to >3 x baseline measurements.
- Discontinue if ALT or AST increase >2 x baseline measurements AND the increase is accompanied by a concomitant increase in TBL to >2 x baseline measurements or the INR concomitantly increases by >0.2 .
- For any patients who present with a constellation of syndromes indicative of liver disease as per the Investigator's overall assessment (ie, fatigue, nausea, vomiting, right upper quadrant pain or tenderness, fever, rash, and/or eosinophilia [$>5\%$]).

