### **7.6.2 Clinical Laboratory Tests**

Central laboratory test results (chemistry, hematology, coagulation, and urinalysis) at each scheduled visit and change from baseline will be summarized with descriptive statistics.

Shift tables from baseline to each scheduled post-baseline visit will be provided for selected chemistry parameters (ALT, AST, ALP, Total Bilirubin, Creatinine, and Creatinine Kinase) and hematology parameters (Hematocrit, Hemoglobin, Platelets, White blood cell count and differential). For chemistry parameters, the following categories will be used: < the lower limit

of normal (LLN), normal,  $>\text{ULN}$  to  $\leq 2 \times \text{ULN}$ ,  $>2 \times \text{ULN}$  to  $\leq 3 \times \text{ULN}$ ,  $>3 \times \text{ULN}$  to  $\leq 5 \times \text{ULN}$ ,  $>5 \times \text{ULN}$ , and missing. For hematology parameters, the following categories will be used: low, normal, high, and missing.

The number and percentage of patients with the following potentially clinically significant abnormal liver function tests at any post-baseline visit will be summarized:

- $\text{ALT} \geq 3 \times \text{ULN}$
- $\text{ALT} \geq 5 \times \text{ULN}$
- $\text{ALT} \geq 10 \times \text{ULN}$
- $\text{AST} \geq 3 \times \text{ULN}$
- $\text{AST} \geq 5 \times \text{ULN}$
- $\text{AST} \geq 10 \times \text{ULN}$
- $\text{ALT}$  or  $\text{AST} \geq 3 \times \text{ULN}$
- Total Bilirubin  $>1.5 \times \text{ULN}$
- Total Bilirubin  $>2 \times \text{ULN}$
- $\text{ALP} \geq 1.5 \times \text{ULN}$
- $\text{ALP} \geq 2 \times \text{ULN}$
- $\text{ALT}$  or  $\text{AST} \geq 3 \times \text{ULN}$  and Total Bilirubin  $>1.5 \times \text{ULN}$
- $\text{ALT}$  or  $\text{AST} \geq 3 \times \text{ULN}$  and Total Bilirubin  $>2 \times \text{ULN}$
- Potential Hy's Law cases:  $\text{ALT}$  or  $\text{AST} \geq 3 \times \text{ULN}$  and Total Bilirubin  $>2 \times \text{ULN}$ , and  $\text{ALP} \leq 2 \times \text{ULN}$

A listing of patients with any post-baseline clinically significant abnormal liver function tests will be presented.

All clinical laboratory data will be listed. Values outside the normal ranges will be flagged.

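### SAP 7.6.2 counts liver-test thresholds after baseline without regard to baseline, so an eligible patient whose values never change can be tabulated as a potential Hy's Law case

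*SAP*

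**What the plan says.** SAP 7.6.2 plans counts and percentages of patients with "potentially clinically significant abnormal liver function tests at any post-baseline visit will be summarized". There are 14 lines:

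- ALT at or above 3x, 5x and 10x ULN, and the same three for AST
- either ALT or AST at or above 3x ULN
- total bilirubin above 1.5x and above 2x ULN
- ALP at or above 1.5x and 2x ULN
- ALT or AST at or above 3x ULN combined with bilirubin above 1.5x, and with bilirubin above 2x ULN
- "Potential Hy's Law cases": ALT or AST at or above 3x ULN, bilirubin above 2x ULN and ALP no higher than 2x ULN.

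None of them carries a baseline condition. The same section also plans change-from-baseline summaries, single-analyte shift tables that include ALT, AST, ALP and total bilirubin, a listing of patients with post-baseline liver abnormalities, and listings of all laboratory data. SAP 7.6 sets the ITT/Safety Population as the basis. SAP 7.1.3 defines baseline as the last pre-dose assessment.

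In Protocol 4.2, exclusion 6 removes ALT or AST of 5x ULN or more. Exclusion 7 removes total bilirubin above 3x ULN, "unless isolated hyperbilirubinemia or due to documented Gilbert's disease". No criterion limits ALP. Exclusion 3 does not close the gap for patients without cirrhosis: "The Child-Pugh score of >6 is applicable to patients with hepatic dysfunction and cirrhosis only". Exclusion 12 leaves a judgement to the investigator: "Any other condition or laboratory abnormality that, in the opinion of the Investigator, would put the patient at unacceptable risk".

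Protocol Appendix D has a separate rule set, headed "For patients with elevations in baseline transaminases or bilirubin", whose transaminase and bilirubin limits are multiples of the patient's own baseline.

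**The concern.** The entry limits and the table thresholds overlap. A patient may enter already meeting a liver criterion, show no change on treatment, and still be counted as meeting it after baseline. The combined lines matter most. A count on the Hy's Law line draws attention in any safety report, there is no control arm against which to judge it, and with about 15 patients a single count is visible. On that line a patient who met the combination at entry cannot be told apart from one who developed it on treatment.

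Elsewhere the plan does take baseline into account. Protocol 8.1 treats a laboratory abnormality present at Screening as an adverse event only if it worsens significantly, and SAP 7.6.1 defines treatment emergence for adverse events. The liver criteria have no equivalent.

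**Working it through.** The plan states no figure on this point, so there is none to reproduce. The check compares the entry limits with the thresholds.

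**Inputs.** Entry limits from Protocol 4.2: ALT and AST below 5x ULN, bilirubin up to 3x ULN (setting aside the exceptions, which only widen the range), ALP unlimited. Thresholds from SAP 7.6.2. Planned size of about 15 from SAP 5.

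**Step 1: which lines can be met within the entry limits** (values in multiples of ULN)

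| SAP 7.6.2 lines | Number | Can be met at entry? |
|---|---|---|
| ALT ≥3; AST ≥3; either ≥3 | 3 | Yes, 3 to <5 |
| ALT ≥5, ≥10; AST ≥5, ≥10 | 4 | No |
| Bilirubin >1.5; >2 | 2 | Yes, up to 3 |
| ALP ≥1.5; ≥2 | 2 | Yes, no limit |
| ALT/AST ≥3 with bilirubin >1.5; with bilirubin >2 | 2 | Yes |
| Potential Hy's Law | 1 | Yes: ALT/AST 3 to <5, bilirubin >2 to 3, ALP ≤2 |

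Total that can be met: 3 + 2 + 2 + 2 + 1 = 10 of 14.

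**Step 2: an unchanged patient.** Take ALT 4, AST 4, bilirubin 2.5 and ALP 1.8 at entry and throughout. Exclusions 6 and 7 do not bar this patient. Lines counted as written: three transaminase lines, two bilirubin lines, one ALP line (≥1.5), two combinations and Hy's Law, which is 3 + 2 + 1 + 2 + 1 = 9 of 14. If a line counts only when it was not met at baseline, the result is 0 of 14. Against Appendix D's multiples the fold change is 1.0, which does not exceed 2. Because a single post-baseline visit is enough, a patient who is improving is also counted if the first sample still meets the line.

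**Step 3: size, as illustration.** One such patient among 15 gives 1/15 = 6.7% (exact 95% CI 0.2% to 31.9%). None gives 0/15 (0% to 21.8%, the upper limit being 1 − 0.025^(1/15)). The SAP plans no interval for this table; these only show how little 15 patients can say either way.

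The documents give no share of entrants who already meet the Hy's Law combination. Assuming a share q, the chance of at least one among 15 is 1 − (1 − q)^15:

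| Assumed q | Chance of at least one |
|---|---|
| 1% | 14% |
| 2% | 26% |
| 5% | 54% |
| 10% | 79% |
| 20% | 96% |

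**Step 4: do the other planned outputs repair the count?** The shift tables take one analyte at a time, so they cannot show whether a combination is new. Their cut-points also differ: they have no 1.5x or 10x boundary, and they use above 3x where the threshold lines use at or above 3x. Change-from-baseline summaries are likewise by analyte. The listings hold what is needed, but the reader must reconstruct baseline status by hand, and the printed count stays as it is.

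**The case against.** The strongest reply is that an inclusive post-baseline screen is a legitimate choice when read with the shift tables, change from baseline and listings. With about 15 patients, anyone on the Hy's Law line can be looked up individually. Under Protocol 8.1 an unchanged abnormality should not appear as a hepatic adverse event, and the study stopping rule uses related adverse events of Grade 2 or higher, not this table. Appendix D governs monitoring and discontinuation of individual patients, and nothing requires a tabulation to mirror it. All of this stands. It limits the harm, chiefly for single analytes, and it means there is no contradiction between the SAP and Appendix D. It does not make the combined counts interpretable as printed.

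A reader might also infer that the table misses a marked rise in a patient who is already elevated. The documents do not support that. An entrant at 4x ULN whose ALT reaches 6x or 12x is newly counted on the 5x line or on both the 5x and 10x lines. For bilirubin and ALP the shift-table bands extend to above 5x ULN, and change from baseline is summarised as well.

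**Conclusion.** The point holds for 10 of the 14 lines and matters for the two combinations and the Hy's Law line. The overlap follows directly from the text. How often it will occur is unknown: 1/15 instead of 0/15 is an illustration, not a forecast, and investigator judgement under exclusion 12 may keep some of these patients out. That the ALT/AST 5x and 10x lines cannot be met at entry assumes that values within the limits at Screening are still within them at the last pre-dose sample.

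A reader might go further and infer that the plan reports unchanged patients as liver injury caused by the drug. It does not. The labels say potential, no attribution is made, and the SAP gives this table no special prominence. The defect is narrower: the counts mix findings present at entry with findings that emerged on treatment.

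**What to change.** In SAP 7.6.2, keep the Safety Population denominator and split each liver criterion, at minimum the two combinations and the potential Hy's Law line, into two rows:

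1. patients who did not meet the criterion at baseline (as defined in SAP 7.1.3) and met it afterwards
2. patients who already met it at baseline.

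Base any statement about liver safety on the first row. Line-specific denominators are unnecessary; with about 15 patients they would only make the table harder to read.

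For patients with abnormal baseline values, add a descriptive count by multiple of baseline, using those already in Appendix D: ALT or AST above 2x, 3x and 5x baseline, bilirubin above 2x baseline, and ALT or AST with bilirubin both above 2x baseline. This is tabulation only and changes no entry, monitoring or discontinuation rule.

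The cost is SAP wording, some table programming and a few extra rows with small counts. All the values are already collected.

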### **7.6.3 Vital Signs**

Descriptive statistics will be provided for vital sign data (systolic and diastolic blood pressure, heart rate, respiratory rate, body temperature, and oxygen saturation) presented as both actual values and changes from baseline over time.

A listing of all vital signs will be provided by patient.

### **7.6.4 Electrocardiograms**

Descriptive statistics will be provided for 12-lead ECG interval data (Heart rate, PR, QRS, QT, and RR) and changes from baseline for each scheduled visit.

All 12-lead ECG findings will be listed by patient.

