4.1 Inclusion Criteria

Patients must meet all of the following criteria to be eligible for study entry:

1. Male or female aged 18 years and above
2. Limited or no treatment options due to resistance, contraindication, intolerance or lack of clinical response to standard of care antifungal therapy, as advocated by the relevant regional/country treatment guidelines
3. Established mycological and clinical diagnosis of candidemia and/or invasive candidiasis from a sample taken <120 hours (for candidemia) or <168 hours (for invasive candidiasis without candidemia) before study qualification:

a. Candidemia criteria

- i. ≥ 1 blood culture positive for yeast/*Candida* spp. identified as *C. auris*;
plus:
 - ii. Clinical signs attributable to candidemia within the 120 hours prior to qualification for the study, to include at least one of the following: (a) fever ($>38^{\circ}\text{C}$), or (b) hypothermia ($<36^{\circ}\text{C}$), or (c) hypotension (SBP $<90\text{mmHg}$ or decrease of $>30\text{mmHg}$);

b. Invasive candidiasis criteria

- i. ≥ 1 specimen (e.g., tissue, aspirate/fluid) sampled aseptically from a normally sterile site culture positive for yeast/*Candida* spp. identified as *C. auris*;
plus:

- ii. Clinical signs attributable to invasive candidiasis within the 168 hours prior to qualification for the study, to include at least one of the following: (a) fever ($>38^{\circ}\text{C}$), or (b) hypothermia ($<36^{\circ}\text{C}$), or (c) hypotension (SBP $<90\text{mmHg}$ or decrease of $>30\text{mmHg}$), or (d) signs associated with organ/site infected with *Candida* (e.g. eye, intra-abdominal).
- 4. Patients with single *C. auris* infection, or mixed *Candida auris* plus other *Candida* spp. (other than *C. krusei*) infection, are eligible for the study.
- 5. Able to have pre-existing intravascular catheters removed and replaced (if necessary)
- 6. Females of childbearing potential with male partners, and males with female partner(s) of childbearing potential, must agree to use 2 forms of highly effective contraception, 1 of which must be a barrier method, throughout the duration of the study and for 90 days following the last study drug administration. Acceptable barrier forms of contraception are condom and diaphragm. Acceptable non-barrier forms of contraception for this study are oral contraceptives (e.g. oral birth control pill, depot, patch, or injectable), abstinence, intrauterine device, and/or spermicide.

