Clinically significant abnormal laboratory or other examination (e.g., ECG) findings that are detected during the study or are present at Screening and significantly worsen during the study should be reported as adverse events. The Investigator will exercise his or her medical and scientific judgment in deciding whether an abnormal laboratory finding or other abnormal assessment is clinically significant. Clinically significant abnormal laboratory values occurring during the clinical study will be followed until repeat tests return to normal, stabilize, or are no longer clinically significant. Any abnormal test that is determined to be an error does not require reporting as an adverse event. A laboratory finding that is abnormal but not clinically significant (e.g., does not warrant intervention) is not considered an adverse event.

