9.2.1.3 Analysis of Safety

All safety analyses will be performed on the Safety Population. Safety data will be subject to clinical review and summarized by appropriate descriptive statistics. A DSMB will be assigned to monitor safety on an ongoing basis throughout the study.

Analyses will be based on adverse events, vital signs, clinical laboratory assessments, and ECGs. Safety analyses will be descriptive and will be presented in tabular format with the appropriate summary statistics.

A TEAE is defined as an adverse event started on or after the administration of study drug. The number and percentage of patients with TEAEs will be tabulated by system organ class, preferred term, and by severity and relationship to treatment. Serious adverse events and adverse events leading to discontinuation from study drug will be summarized. Listings will also be provided for SAEs and adverse events leading to discontinuation of study drug.

Descriptive statistics will be provided for clinical laboratory data for both actual values and changes from baseline over time.

Descriptive statistics will be provided for vital sign data presented as both actual values and changes from baseline over time.

Abnormal physical examination findings will be listed.

Descriptive statistics will be provided for ECG interval data and presented as both actual values and changes from baseline.

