APPENDIX A: SCHEDULE OF PROCEDURES (CONT'D)

Procedure	Eligibility	Screening (≤120 or ≤168 Hours of Baseline)[a]	Treatment Period[b]			Follow-up		Early Termination
			Baseline (Day 1 Pre-Dose)	Study Drug Treatment (≤42 Days)	End of Study Drug Treatment (EOST)[c]	Follow-up 2 Weeks After EOST +2 Days	Follow-up 4 Weeks After EOST +4 Days	
Other cultures and histopathology[h,r]	X[u]	X[u]	X	X	X	X	X	X
Imaging tests[h,r]	X[u]	X[u]	X	X	X	X	X	X
Pharmacokinetic sample[q]			X	X	X	X		X
Serum sample[s]			X		X			X
Evaluation of treatment outcome					X	X	X	X
Study drug administration[t]				X				
Prior/concomitant medications		X	X	X	X	X	X	X
Adverse event evaluation		X	X	X	X	X	X	X

- a. To be completed within 120 hours (for candidemia) or 168 hours (for invasive candidiasis without candidemia) from blood or tissue/fluid/aspirate sampling time for culture positive for *Candida* spp.
- b. For outpatients during Study Drug Treatment, twice weekly visits are required with a maximum window of ±2 days. Patients will be asked to record daily dosing on a diary and to bring the diary and study drug bottles with them to every clinic visit.
- c. End of Study Drug Treatment (EOST) occurs after completion of APX001 dosing.
- d. To be obtained prior to the initiation of any protocol-specific procedure outside of SOC.
- e. Vital signs will include temperature, blood pressure, heart rate, respiratory rate, oxygen saturation, and weight. Vital signs will be collected at Screening, Baseline (pre-dose), daily on Study Days 1 to 4, and twice weekly thereafter for outpatients (daily while inpatient) during Study Drug Treatment, EOST, and 2 and 4 weeks after EOST, or Early Termination. Height will be collected (from the patient's medical record) at Baseline.
- f. Intravascular catheters logged until EOST while inpatient, and as clinically indicated thereafter or for outpatients.
- g. If possible, all indwelling intravascular catheters should be removed and the catheter tips cultured prior to starting APX001 dosing. The entrance site should also be cultured if it appears infected. Any removed catheter tip should be sent for culture.
- h. As clinically indicated.
- i. (* Baseline dilated fundoscopy may be performed up to Day 3 of study) Only required in those patients who had positive fundoscopic findings up to Day 3 or as clinically indicated.

Footnotes from appendix above (cont'd)

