#### **6.4.5.5 *Electrocardiograms***

A 12-lead ECG will be obtained at Baseline (pre-dose), EOST, and 4 weeks after EOST, or Early Termination.

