### **7.1.3 Baseline Definition**

For microbiological data, baseline pathogen(s) are *Candida auris* isolated from the last positive blood sample collected within 120 hours (for candidemia) or last positive culture from a specimen (e.g., tissue, aspirate/fluid) sampled from a normally sterile site within 168 hours (for invasive candidiasis without candidemia) prior to qualification for the study.

For all efficacy and safety endpoints, baseline is defined as the last measurement or assessment prior to the first dose of study drug.

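### SAP 7.6.4 summarises QT and its change from baseline without rate correction, so a fall in heart rate on recovery can appear as QT lengthening (minor, cheap to fix)

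*SAP*

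**What the plan says.** SAP 7.6.4 names the variables: "Descriptive statistics will be provided for 12-lead ECG interval data (Heart rate, PR, QRS, QT, and RR". Change from baseline is summarised at each scheduled visit. The same section adds: "All 12-lead ECG findings will be listed by patient".

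Protocol 9.2.1.3 is less specific: "Descriptive statistics will be provided for ECG interval data and presented as both actual values and changes from baseline". It names no interval. Neither document gives a QT correction formula, a corrected QT variable or a QT category.

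The schedule in SAP 6.4.5.5 is: "A 12-lead ECG will be obtained at Baseline (pre-dose), EOST, and 4 weeks after EOST, or Early Termination". Protocol Appendix A, footnote c, places the second of these visits: "End of Study Drug Treatment (EOST) occurs after completion of APX001 dosing". Baseline is set in SAP 7.1.3: "For all efficacy and safety endpoints, baseline is defined as the last measurement or assessment prior to the first dose of study drug".

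The study is single-arm (SAP 2.2), with approximately 15 patients (SAP 5).

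**The concern.** QT shortens as heart rate rises and lengthens as it falls, so a change in raw QT is interpretable only if the rate is similar at both visits. Here there is reason to expect that it may not be.

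For candidemia, Protocol 4.1 requires "Clinical signs attributable to candidemia within the 120 hours prior to qualification for the study, to include at least one of the following": fever, hypothermia or hypotension. Protocol 4.3 has dosing start within 12 hours of qualification. The pre-dose ECG is therefore taken near an acute illness, and the next scheduled ECG comes when treatment has ended, up to 42 days later. No control arm shares the same shift and allows it to be subtracted.

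Safety is part of the primary objective (Protocol 2.1; SAP 2.1.1). As written, the only tabulated QT change mixes any drug effect with the change in rate. If rates fall with recovery, the table will tend to show QT lengthening that the drug did not cause.

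**Working it through.** **What can be reproduced.** The documents state no QT, QTc or heart-rate figure, so there is nothing to reproduce. The check asks how far raw QT moves when only the heart rate changes.

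**Inputs.** From the documents: the variable list (SAP 7.6.4), the baseline definition (SAP 7.1.3) and the visit schedule (SAP 6.4.5.5). Assumed: QTc (c) = 420 ms and heart rates (h) of 80 to 110 bpm.

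**Formulas.** RR = 60/h in seconds. For a constant QTc of c, raw QT is:
- Fridericia: c × RR^(1/3)
- Framingham: c - 154 × (1 - RR)
- Bazett: c × RR^(1/2)
- Hodges: c - 1.75 × (h - 60)

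**Raw QT (ms) with no drug effect, c = 420.**

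| Relation | 110 bpm | 100 bpm | 80 bpm | Change 100 to 80 | Change 110 to 80 |
|---|---|---|---|---|---|
| Fridericia | 343.2 | 354.2 | 381.6 | +27.4 | +38.4 |
| Framingham | 350.0 | 358.4 | 381.5 | +23.1 | +31.5 |
| Bazett | 310.2 | 325.3 | 363.7 | +38.4 | +53.5 |
| Hodges | 332.5 | 350.0 | 385.0 | +35.0 | +52.5 |

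The assumed QTc matters little. For 110 to 80 bpm and c from 390 to 450 ms, the Fridericia change is 35.7 to 41.2 ms and the Bazett change 49.7 to 57.4 ms. The Framingham and Hodges changes do not depend on c.

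**Opposite direction.** Suppose the rate rises from 80 to 100 bpm. The true QTc increase that leaves raw QT unchanged is:
- Fridericia: 420 × (1.25^(1/3) - 1) = 32.4 ms
- Framingham: 154 × (0.75 - 0.60) = 23.1 ms
- Bazett: 420 × (1.25^(1/2) - 1) = 49.6 ms
- Hodges: 1.75 × 20 = 35.0 ms

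Masking is therefore arithmetically possible, but only when the follow-up rate is above the baseline rate.

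**Does QTcF help if Fridericia is not the true relation?** Take 110 to 80 bpm and divide each raw QT above by RR^(1/3), which is 0.8171 at 110 bpm and 0.9086 at 80 bpm. The spurious QTcF change that remains is:
- Fridericia true: 0
- Framingham true: 428.4 to 419.9, or -8.5 ms
- Bazett true: 379.6 to 400.3, or +20.7 ms
- Hodges true: 406.9 to 423.7, or +16.8 ms

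The residual runs from -8.5 to +20.7 ms, against +31.5 to +53.5 ms for raw QT. QTcF reduces the artefact under all four relations but does not always remove it.

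**The case against.** The strongest reply is that little depends on this table, and most of that reply stands.

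- **The data are available.** Heart rate and RR are summarised beside QT, ECG findings are listed by patient, and SAP 10 promises listings of all available data. At three scheduled ECGs for about 15 patients there are roughly 45 tracings, so QTc can be worked out by hand. This stands as a reason for a low rating. It does not replace a planned result: visit means of QT and RR do not give the mean QTc or each patient's change, and a later hand calculation leaves the formula and categories to be chosen after the data are seen.
- **The schedule is sparse.** The only scheduled ECGs after baseline fall once dosing is complete and 4 weeks later, or at Early Termination. This stands. Correction improves the summary but does not make it a strong test of drug effect.
- **Another route exists.** Protocol 8.1 has the following reported as adverse events: "Clinically significant abnormal laboratory or other examination (e.g., ECG) findings that are detected during the study". This stands, although it rests on investigator judgment and leaves the table as it is.
- **The programming specifications may add QTc.** SAP 10 places these in a separate document that cannot be checked here. That is possible, but SAP 7.6.4 sets its own list and QTc is not on it.
- **The size is assumed.** This is correct. Tachycardia is not an entry criterion, the qualifying signs may precede the ECG by days, and Protocol 4.1 admits invasive candidiasis on site-specific signs alone.

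A reader might infer that the table is as likely to hide true prolongation as to exaggerate it. The documents do not support equal weight. Masking needs a rate above baseline, for example in a deteriorating patient at Early Termination, whereas recovery would usually be expected to lower the rate.

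**Conclusion.** The concern holds as a minor point. SAP 7.6.4 summarises raw QT and its change from a baseline taken near acute infection, without rate correction and without a control arm. If heart rate falls with recovery, raw QT lengthens with no drug effect. The illustrative size is 27 ms for 100 to 80 bpm (23 to 38 ms) and 38 ms for 110 to 80 bpm (32 to 54 ms). These figures rest on an assumed QTc of 420 ms, assumed heart rates and four standard rate relations; none comes from the documents.

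A reader might also infer that APX001 has a QT problem or that ECG safety goes unmonitored. Neither follows. The documents report no QT signal, ECGs are collected and listed, and clinically significant findings become adverse events. No efficacy endpoint uses QT, and no stated stopping rule names it. The gap lies in the planned summary, not in data collection.

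**What to change.** In SAP 7.6.4:

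1. Derive QTcF = QT / RR^(1/3), with RR in seconds, for each ECG from the QT and RR already collected.
2. Report QTcF value and change from baseline at each scheduled visit as the main QT result, and keep raw QT as supportive.
3. Add patient counts by category of QTcF value and of QTcF change. The documents give no cut-offs, so the sponsor should fix them in the SAP before database lock.

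The cost is a few lines of SAP text, one derivation and a few table rows. No procedure, visit or aspect of patient management changes. The downside is the residual error shown above if Fridericia is not the true rate relation. Keeping raw QT, RR and heart rate in the tables lets a reader judge it.
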